**Lay Summary of Proposed Research**

**Lay Summary of Proposed Research**

This proposal describes a combined laboratory and clinical trial preliminary investigation to advance medication development for cocaine dependence. The main objective is to test whether intranasal oxytocin could reduce relapse risk by reducing stress sensitivity. To measure stress sensitivity, this study will evaluate a new stress challenge: a) intranasal desmopressin, a vasopressin analog, will be used as an endocrine stressor; its effects will be evaluated by serial measurements of serum Adrenocorticotropin hormone

---

(ACTH), and self reports; b) if pretreatment with intranasal oxytocin dampens the ACTH and subjective response to intranasal desmopressin. These measures will be tested during a 7-day inpatient abstinence induction hospitalization. For those patients with family and work obligations, an outpatient abstinence induction procedure is available. The response to the desmopressin challenge will be compared to a cohort of matched control subjects. After abstinence induction, cocaine dependent patients enter a 6-week, double-blind, randomized, placebo-controlled trial of 24 IU of intranasal oxytocin vs. placebo, to monitor if this reduces the relapse risk.

This study is based on the findings that chronic stress, caused in these patients by cocaine dependence, increases the sensitivity of the Hypothalamo-Pituitary-Adrenal (HPA) axis and CNS stress pathways to vasopressin. For their part, oxytocin systems, in chronic stress, acquire an increasing moderating effect on CNS stress systems and the HPA axis. Cocaine dependence generates increased responsivity of stress systems to oxytocin in the face of depleted oxytocin stores; thus creating an environment where exogenous oxytocin could exert a strong regulatory effect. Intranasal administration provides a convenient to deliver these small peptides to the brain. Studying the feasibility of this approach, and its applicability to the treatment of cocaine-dependent patients, will be a goal of this study.

The main outcome of this study will be the number of consecutive days of abstinence from cocaine after abstinence induction. A secondary outcome will be whether the acute effect of intranasal oxytocin on desmopressin-induced ACTH secretion is associated with the number of days of continued abstinence.

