## Specific Aims and Hypotheses

### Specific Aims and Hypotheses

**Primary Aim 1 [Phase 1]:** The goal of primary aim 1 is to investigate the effect that both IN DDAVP and OT have on stress sensitivity. *Primary Aim 1a, hypothesis 1:* IN DDAVP will be associated with greater secretion of ACTH and subjective ratings in cocaine dependent patients compared to control patients. *Primary Aim 1b, hypothesis 2:* IN OT treatment will significantly reduce the secretion of ACTH and subjective ratings associated with IN DDAVP in cocaine dependent patients compared to control patients. The differences based on the outcomes specified in hypotheses 1 and 2 between the subjects in COC and CON groups will be examined

using parametric or non-parametric matched sample test.

**Primary Aim 2 [Phase 2]:** The goal of primary aim 2 is to investigate the effect of OT on cocaine use after abstinence induction. Primary Aim 2, hypothesis 1: Cocaine-dependent patients receiving IN OT will display significantly more days of consecutive abstinence after abstinence induction compared with IN placebo at the end of the study. The effect of IN OT treatment (based on groups) on the primary outcome (maximum number of consecutive abstinence days for each patient) will be analyzed using generalized linear models (PROC GLIMMIX in SAS®) with main effect of randomization assignment (OT vs. PBO).

**Secondary Hypotheses:** We will examine the feasibility, safety, tolerability, and potential efficacy of IN OT for relapse prevention in cocaine dependence. 2.1): Cocaine-dependent patients receiving IN OT who complete all 6 weeks of phase 2 will tally fewer cocaine using days than placebo patients who complete all 6 weeks. 2.2): Cocaine-dependent patients receiving OT who relapse will tally fewer cocaine using days than patients receiving placebo who relapse. Regression analysis will be implemented using those who complete (2.1) and those who relapse (2.2) to test the effect of OT on the secondary outcome (cocaine using days).

**Exploratory Aims:** We will investigate a) if the acute reduction in stress sensitivity with IN OT in Phase 1 or at the end of Phase 2 (repeat IN DDAVP challenge) is associated with a greater number of days of continued abstinence from cocaine in Phase 2; b) if there are gender effects on the primary outcomes.

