Study Assessments: (Table 1). **Physiological tests:** 1) *urine toxicology:* this will be estimated qualitatively at every visit by dipstick (Iscreen™, 9 drugs) which indicates the presence of cocaine, amphetamine, metamphetamine, cannabis, methadone, morphine, oxycodone, barbiturate, benzodiazepine. 2) *stress sensitivity testing:* as outlined in table 2, it is performed on two separate days, [in counterbalanced order.] Day 1: an endocrine challenge with IN DDAVP 80IU (de Goeij et al., 1991). After establishing baseline ACTH secretion, serum samples are taken at time points extending to 90 minutes. The DDAVP challenge is also repeated at the end of phase 2, to see if ACTH secretion is affected by 6 weeks of IN OT administration. Day 2 tests if pretreatment with IN OT treatment can acutely dampen the effect of DDAVP on ACTH secretion. After baseline is measured before and after IN OT, serum samples for ACTH are taken at time points extending to 90 minutes. Serum samples are spun, frozen at -20 Celsius, packed in dry ice, and shipped to the Nathan Kline Laboratory in Orangeburg, NY. 3) Medical monitoring: week 2,4,6: Na, K, Cl, CO3, spot cortisol, β-HCG for women. **Clinician Interviews:** 1) TLFB (Litten and Allan, 1992; baseline, each visit in phase 2). This is an adaptation of the alcohol TLFB, which estimates cocaine use in the past 30 days at baseline, and is then repeated at every visit with the aid of a calendar to obtain a day-by-day registry of cocaine use during phase 2. 2) CGI-O, (Guy, 1976; baseline, weekly during phase 2) the severity and improvement scales measure the overall clinical status of the subject and change from baseline. 3) BAS (Chaplin et al., 2010). This scale is used during stress sensitivity testing. Research staff rate participants on 13 items of behavior relating to arousal during the stress challenge. 4) Adverse event form is a check-list of side effects experienced by participants; 5) HamD, (Williams, 1988; baseline, each wk in phase 2). Estimates 25 depression symptoms. **Self reports:** 1) PSS (Cohen et al., 1983; baseline, weekly during phase 2) measures monthly situations in a subject's lives deemed stressful. Ten questions are scored between 0 (never) to 4 (very often). Modified, it will be administered weekly during phase 2, [and will include a open-ended question inquiring about any adverse life event in the past week.] 2) *Subjective ratings of cocaine craving, depression, anxiety, stress during stress testing (Likert scale 0 to 10, 10 = worse), performed during stress sensitivity testing.* 3) CCS (Weiss et al., 1997) 3-item questionnaire rating cravings for cocaine on a scale of 0 (none) to 9 (Strong).

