
3.3 Compensation and data management.

For phase 1, control participants will receive \$150 for their participation; cocaine-dependent patients will receive \$20/day, or will receive \$150 if they complete the whole week. [During phase 2, cocaine-dependent patients accumulate vouchers for completing all study procedures (Bringing home bottle, assessments, study visits).] Each visit with all study procedures completed will earn them \$5. They can also earn \$20 for each week of consecutive and complete participation. Transportation costs are covered (\$5/visit). Total earnings can reach \$450. StudyTrack, a software system for clinical trials will be used for data management.

3.4 Statistical Analysis:

3.4.1. Outcome measures: PHASE 1: **Primary outcomes:** 1) secretion of ACTH (continuous measure of area from the concentration-time curve (AUC) using trapezoid method, pg/mL/min). 2) subjective rating of cocaine craving, stress, depression, anxiety (continuous) 3) difference in ACTH secretion between IN DDAVP (day 1) and IN OT prior to IN DDAVP (day 2) (continuous measure); 4) difference in subjective rating of cocaine

craving, stress, depression, anxiety between IN VP (day 1) and IN OT prior to IN DDAVP (day 2; continuous, controlled for last day of use before entering Phase 1); **PHASE 2: Primary outcome:** 1) maximum number of consecutive abstinent days (continuous measure) ; **Secondary outcome:** 1) cocaine using days (continuous). **Covariates/Predictor Variables:** demographics, age, gender; cocaine data (TLFB, 30 days; IN vs. smoked).

3.4.2. Sample size: In PHASE 1, we will enroll a total of 100 participants: 1) Cocaine group (COC): Cocaine-dependent patients seeking treatment (n=50); 2) Control group (CON): Healthy matched controls (n=50), each matched demographically (see 3.1.1). In PHASE 2, we will randomize the 50 COC patients into two groups: 1) Oxytocin group (OT), n=25; 2) Placebo group (PBO), n=25. An independent statistician will perform, and an independent pharmacist will implement the randomization. Individuals will be stratified by route of cocaine use. The randomization will be balanced in blocks of random size 2 and 4 to prevent compromise of the blind.

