3.4.3. Intent to Treat/ Dropouts and missing data: All primary analysis will be on Intent-to-Treat (ITT) sample, i.e. all subjects from COC and CON groups in Phase 1 (50 per arm) and all subjects randomized to OT and PBO groups in Phase 2 (25 per arm). [In Phase 1, we expect little attrition. Measures as described (3.4.1) will provide usable data after 2 days of measurements. For phase 2, we anticipate an attrition rate of 30%, leaving approximately 18 completers per arm.] If a patient drops out during Phase 2, the maximum number of consecutive abstinent days achieved in the trial will be considered as primary outcome. The inferences from analyses with missing data are considered valid provided that they are "missing at random" (Little and Rubin 1987). One can assume either parametric or semi-parametric models for missingness (Diggle and Kenward 1994; Kenward 1998; Liu et al 1999; Rotnitzky et al 1998). Inferences from various models of missingness provides a measure of the efficacy estimate from each models.

3.4.4. Significance testing and preliminary analyses: All tests for main effects will be performed at two-tailed significance $\alpha=5\%$. Before performing specific analyses (described below), we will examine all variables for outliers and normality. Demographic variables (ethnicity, gender, age) and baseline measures in the groups will be described in terms of means, standard deviations, proportions and 95% confidence intervals. The covariates (Section 3.4.1) will be included if they are found to affect outcome measures.

Hypotheses:

Primary Aim 1 [Phase 1]: The goal of primary aim 1 is to investigate the effect that both IN DDAVP and OT have on stress sensitivity. **Primary Aim 1a, hypothesis 1:** IN DDAVP will be associated with greater secretion of ACTH and subjective ratings in cocaine dependent patients compared to control patients. **Primary Aim 1b, hypothesis 2:** IN OT treatment will significantly reduce the secretion of ACTH and subjective ratings associated with IN DDAVP in cocaine dependent patients compared to control patients. The differences based on the outcomes specified in hypotheses 1 and 2 between the subjects in COC and CON groups will be examined using parametric or non-parametric matched sample test.

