The primary outcome was maximum number of consecutive cocaine abstinent weeks. Cocaine use was determined using urine toxicology and TLFB self-report. In a given week, cocaine use was defined as positive if any urine toxicology tests or TLFB self-report was positive (regardless if urine toxicology was negative or missing). Cocaine use was defined as negative if both urine toxicology and self-report were negative or if urine toxicology was missing, the self-report was negative. Cocaine use status was defined as missing if both urine toxicology and self-report were missing. Wilcoxon rank-sum tests were used to examine differences in maximum number of consecutive cocaine abstinent weeks by medication group.

Twenty-six cocaine patients were randomized to 6 weeks of Oxytocin (n=15) or Placebo (n=11). The median (IQR) of the maximum number of consecutive abstinent weeks was 1.0 (1.0 to 1.0) for the OT group and 1.0 (1.0 to 2.0) for the PBO group. The Wilcoxon rank-sum test was not significant, there was no effect of treatment arm on the maximum number of consecutive abstinent weeks ($W = 144.5, p = .67$).

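### The Phase 2 primary analysis planned in abstinent days by GLIMMIX is reported in abstinent weeks by Wilcoxon, with no reason given, and the printed W and p do not fit 26 patients with the printed quartiles

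*SAP*

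**What the plan says.** **Planned outcome.** The Protocol's Lay Summary states: "The main outcome of this study will be the number of consecutive days of abstinence from cocaine after abstinence induction". Specific Aims, Primary Aim 2, makes this "maximum number of consecutive abstinence days for each patient". SAP 3.4.1 lists the same outcome, in days, as a continuous measure.

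**Planned test and analysis set.** Primary Aim 2, in both documents, names a generalized linear model (PROC GLIMMIX) with a main effect of arm. SAP 3.4.3 puts all primary analyses on the intent-to-treat sample, meaning everyone randomised. It also keeps dropouts in: "the maximum number of consecutive abstinent days achieved in the trial will be considered as primary outcome".

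**Reported.** The closing SAP section, headed Primary outcome, is in the past tense and says: "The primary outcome was maximum number of consecutive cocaine abstinent weeks". It uses Wilcoxon rank-sum tests. It gives 26 randomised (15 oxytocin, 11 placebo), medians (IQR) of 1.0 (1.0 to 1.0) and 1.0 (1.0 to 2.0) weeks, W = 144.5 and p = .67. It does not state the numbers analysed, the arm to which W belongs, or how p was computed.

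**The concern.** Both the unit of the outcome and the test changed between plan and report. The closing section gives no reason or date, so a reader cannot tell whether the choice came before or after unblinding. Within these documents the comparison that was planned has no result.

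The change of unit also discards information. Over 42 days the daily score can take 43 values (0 to 42) and the weekly score 7 (0 to 6). If all 26 patients contribute, the printed quartiles force at least 8 oxytocin and 4 placebo patients, 12 in all, onto the same score of 1 week. Any differences in days among those 12 go unused.

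The second problem is separate. The one primary result that is reported cannot be reproduced from the figures printed beside it.

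**Working it through.** **Inputs** (SAP, Primary outcome): n = 15 and 11, N = 26; the medians and IQRs above; W = 144.5; p = .67. SAP 3.4.4 makes tests two-sided. Assumption: whole-week scores from 0 to 6, because Phase 2 lasts six weeks.

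**Which sum is W?** All ranks add to 26 × 27/2 = 351. The null means are 11 × 27/2 = 148.5 (placebo rank sum), 15 × 27/2 = 202.5 (oxytocin rank sum) and 15 × 11/2 = 82.5 (Mann-Whitney U). I enumerated every set of scores that matches the printed medians and IQRs, using nine quartile definitions and the same definition in both arms.
- The placebo rank sum runs from 137.5 to 195.0.
- The oxytocin rank sum is therefore 351 minus that, or 156.0 to 213.5, which excludes 144.5.
- The placebo U is the rank sum minus 66, or 71.5 to 129.0. The oxytocin U is 165 minus that, or 36.0 to 93.5. Both exclude 144.5.

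So 144.5 can only be the placebo rank sum, 4 below its null mean.

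**Trying to reproduce p.**
- Without ties: SD = √(15 × 11 × 27/12) = 19.27, z = 4/19.27 = 0.21, p = .84.
- With ties: variance = (15 × 11/12) × [27 − Σ(t³ − t)/(26 × 25)].

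Example, as counts at 0, 1, …, 6 weeks: oxytocin (0,12,0,1,2,0,0), placebo (2,5,3,1,0,0,0). The mid-ranks for 0, 1, 2 and 3 weeks are 1.5, 11, 21 and 23.5. Placebo sum = 2 × 1.5 + 5 × 11 + 3 × 21 + 23.5 = 144.5. Σ(t³ − t) = 4938, SD = 16.33, p = .81 (.83 with continuity correction).

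All 608 matching pairs of data sets with W = 144.5:

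| Method | p |
|---|---|
| Tie-corrected normal | 0.790 to 0.821 |
| With continuity correction | 0.816 to 0.843 |
| Exact permutation | 0.776 to 0.909 |

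None gives .67. A looser enumeration, with scores up to 7 and the arms not held to one quartile definition, widens the exact range to 0.71 to 0.91, which still excludes .67. If the quartiles are ignored altogether, no tie pattern on up to 8 score levels gives .67 by normal or t approximation. The nearest are 23 tied values (.71, or .74 corrected) and 24 tied values (.65, or .69 corrected).

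**What would give .67 with all 26?**
- By normal approximation, W from 154.5 to 156.5. Example: oxytocin (0,12,0,1,0,0,2), placebo (0,8,0,1,0,0,2). Placebo sum = 8 × 10.5 + 21.5 + 2 × 24.5 = 154.5, SD = 14.18, z = 6/14.18 = 0.423, p = .672.
- By exact test, other values also work. Oxytocin (0,12,1,0,1,0,1) with placebo (2,6,1,1,0,1,0) gives W = 141.5 and exact p = .672. Oxytocin (3,9,1,0,2,0,0) with placebo (2,5,3,1,0,0,0) gives W = 157.0 and exact p = .672.

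**What would fit both printed figures?** Some smaller sets would, such as 13 oxytocin and 11 placebo: oxytocin (1,9,0,0,0,1,2), placebo (1,5,3,0,1,1,0) gives W = 144.5 and p = .674 with continuity correction. The documents state no such sizes.

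**Direction.** At 15/11, W = 144.5 means mean ranks of 144.5/11 = 13.1 for placebo and 206.5/15 = 13.8 for oxytocin. W = 154.5 reverses the order: 14.0 and 13.1.

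**The case against.** **A rank test is defensible.** Scores this heavily tied suit one, and SAP 3.4.4 says "we will examine all variables for outliers and normality". That could at most excuse the test. No fallback test is named for Phase 2; the non-parametric option is written only for the Phase 1 matched comparison. Nor does it explain the unit, since a rank test runs equally well on days.

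**The mismatch may be a typing slip.** W = 154.5 differs from the printed value by one digit and gives .672 with all 26 patients and the printed quartiles. This simple explanation needs no exclusions, and it stands as a possibility. A reader might infer instead that randomised patients were dropped and intent-to-treat was breached. The documents do not support that: the closing section mentions no exclusions. The most that can be asked is that the numbers analysed be stated.

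**The change may have been decided blind.** A reader might infer that weeks were chosen after seeing the results. Nothing shows this. The title pages were not available for review, so the fair statement is only that the closing section itself gives no reason or date.

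**The finding is null either way.** With 26 analysed, that holds. It does not extend to every smaller set that fits the printed W. At 14/11 a few matching data sets have 144.5 as the oxytocin rank sum, with p near .017, although those do not match the printed p.

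**Conclusion.** The change from days by GLIMMIX to weeks by Wilcoxon is plain on the face of the documents and unexplained in them. The planned primary comparison has no result there.

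The printed result is also internally inconsistent. With 15 and 11 patients and the printed quartiles, W = 144.5 implies p of about 0.79 to 0.84 by normal approximation (0.78 to 0.91 exact), not .67. At least one of W, p, n and the IQRs is wrong, or fewer than 26 patients were analysed, and the documents do not show which. The ranges rest on whole-week scores 0 to 6 and one quartile definition for both arms.

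With all 26 analysed the result is non-significant whether the printed W or the printed p is right, so the conclusion of no treatment effect is not shown to change. These are faults of disclosure and reporting in the primary analysis.

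**What to change.** 1. Report maximum consecutive abstinent days by arm on all 26 randomised patients, using the planned GLIMMIX comparison with a 95% CI. Primary Aim 2 names no distribution or link, so say that both were chosen after the fact.
2. Label the weekly Wilcoxon as a post-hoc change unless a dated pre-unblinding decision can be shown.
3. Re-run the rank-sum test on all 26 and correct W and p. State the number analysed per arm, the arm to which W refers and the p-value method.

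Optional clarifications: a rank test on days; a statement on whether a week with missing status breaks a run; and an analysis counting missed visits as use. The Protocol applies that missed-visit rule to the responder rating (Phase 2, item 11), so leaving it out of the primary outcome is not a departure.

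**Cost.** No new data are needed: the TLFB was planned to "obtain a day-by-day registry of cocaine use during phase 2", with urine tested three times a week. The price is analyst time, one unplanned model choice and an imprecise answer. Under an equal-variance t interval the half-width is 2.064 × √(1/15 + 1/11) = 0.82 SD; a GLIMMIX interval for skewed run lengths will differ.

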Primary Aim 2 [Phase 2]: The goal of primary aim 2 is to investigate the effect of OT on cocaine use after abstinence induction. **Primary Aim 2, hypothesis 1:** Cocaine-dependent patients receiving IN OT will display significantly more days of consecutive abstinence after abstinence induction compared with IN placebo at the end of the study. The effect of IN OT treatment (based on groups) on the primary outcome (maximum number of consecutive abstinence days for each patient) will be analyzed using generalized linear models (PROC GLIMMIX in SAS®) with main effect of randomization assignment (OT vs. PBO).

Secondary Hypotheses: We will examine the feasibility, safety, tolerability, and potential efficacy of IN OT for relapse prevention in cocaine dependence. 2.1): Cocaine-dependent patients receiving IN OT who complete all 6 weeks of phase 2 will tally fewer cocaine using days than placebo patients who complete all 6 weeks. 2.2): Cocaine-dependent patients receiving OT who relapse will tally fewer cocaine using days than patients receiving placebo who relapse. Regression analysis will be implemented using those who complete (2.1) and those who relapse (2.2) to test the effect of OT on the secondary outcome (cocaine using days).

Exploratory Aims: We will investigate a) if the acute reduction in stress sensitivity with IN OT in Phase 1 or at the end of Phase 2 (repeat IN DDAVP challenge) is associated with a greater number of days of continued abstinence from cocaine in Phase 2; b) if there are gender effects on the primary outcomes.

Power Analysis: **Primary aim 1:** With 50 cocaine dependent subjects and 50 matched controls, we have 50 matched pairs which give us at least 80% power to detect a significant difference between groups using 2-sided hypothesis test at a 5% level of significance for an effect size $\geq .41$. This is considered a small/medium effect size (Araya et al., 2006; Simeon et al., 2011), which are reasonable to expect based on the existing literature. **Primary aim 2:** In Phase 2, we randomize 50 participants into 2 groups (25 in PBO and 25 in OT). The comparison will achieve at least 80% power (testing 2-sided hypothesis of difference at 5% significance) when detecting an effect size ≥ 0.8 . This is a medium effect size that we based on existing relapse studies in cocaine dependence (Back et al., 2010).

Primary outcome:

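### The SAP concludes no treatment effect from a non-significant test in 15 vs 11 patients, without an estimate or interval, and its W and p do not fit all 26 randomised patients

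*SAP*

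**What the plan says.** **Plan.** The SAP's Power Analysis for Primary aim 2 states: "In Phase 2, we randomize 50 participants into 2 groups (25 in PBO and 25 in OT". It claims at least 80% power, two-sided at 5%, for an effect size of 0.8 or more. Under Primary Aim 2 the outcome and method are: "maximum number of consecutive abstinence days for each patient) will be analyzed using generalized linear models". Section 3.4.3 adds: "All primary analysis will be on Intent-to-Treat (ITT) sample". For patients who leave early it scores the longest run reached: "If a patient drops out during Phase 2, the maximum number of consecutive abstinent days achieved in the trial".

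**Result.** The closing Primary outcome paragraphs report: "Twenty-six cocaine patients were randomized to 6 weeks of Oxytocin (n=15) or Placebo (n=11"). The outcome is now counted in weeks and compared by a Wilcoxon rank-sum test. The summaries, as median (IQR), are "1.0 (1.0 to 1.0) for the OT group and 1.0 (1.0 to 2.0) for the PBO group". The test result is W = 144.5, p = .67, and the conclusion is "The Wilcoxon rank-sum test was not significant, there was no effect of treatment arm on the maximum number of consecutive abstinent weeks".

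A week can have no status: "Cocaine use status was defined as missing if both urine toxicology and self-report were missing". The text does not say how such weeks enter a patient's longest run, how many patients entered the test, or which arm W belongs to.

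**The concern.** There are two linked problems.

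1. A p-value above 5% says that the data did not separate the arms. It does not say that the arms are alike. That needs an estimate of the difference and an interval narrow enough to exclude differences that matter, and neither is printed. With 26 of 50 planned patients, the wording matters more than it would at full size.
2. The two numbers that carry the primary result contradict each other if every randomised patient was tested. Until that is resolved, a reader cannot tell whether W is wrong, p is wrong, or the test used fewer patients than were randomised. The last would need to be reconciled with the intent-to-treat rule.

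**Working it through.** **Inputs** (SAP, Primary outcome): n_O = 15, n_P = 11, N = 26; medians and quartiles 1 (1 to 1) for oxytocin and 1 (1 to 2) for placebo; W = 144.5; p = .67. Planned size and effect (Power Analysis): 25 per arm, 0.8 SD. Assumption: the outcome is a whole number of weeks, 0 to 6.

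**1. The plan's own power figure.** Power ≈ Φ(0.8·√(n₁n₂/(n₁+n₂)) − 1.96).
- 25 vs 25: 0.8 × √12.5 = 2.83, giving 81% (79% by noncentral t). The stated 80% reproduces approximately.
- 15 vs 11: 0.8 × √(165/26) = 2.02, giving 52% (49% by t). This is indicative only, because 0.8 SD was planned for days under a generalized linear model, not for heavily tied weeks under a rank test.

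**2. What W can be.** The untied null variance is n_O·n_P·(N+1)/12 = 165 × 27/12 = 371.25, so SD = 19.27.

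| Reading of W | Null mean | 144.5 minus mean | p, no ties |
|---|---|---|---|
| Placebo rank sum | 11 × 27/2 = 148.5 | −4 | 0.84 |
| Oxytocin rank sum | 15 × 27/2 = 202.5 | −58 | 0.003 |
| Mann-Whitney count | 165/2 = 82.5 | +62 | 0.001 |

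Ties shrink the variance and so make p smaller. The last two rows therefore cannot reach .67. No data set matching the printed medians and quartiles gives 144.5 under those two readings either. Only the placebo rank sum is left.

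**3. Can ties bring 0.84 down to .67?** With ties, the variance is 371.25 × (1 − f), where f = Σ(t³ − t)/(N³ − N) and N³ − N = 17,550. For a deviation of 4 to give a p that rounds to .67, f must be:
- 0.755 to 0.776 without continuity correction (normal or t);
- 0.812 to 0.828 with it.

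Attainable values skip both ranges:
- 23 tied plus 3 tied: (12,144 + 24)/17,550 = 0.693
- 24 tied, with or without a tied pair: 0.786 to 0.787
- 25 tied: 15,600/17,550 = 0.889

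So no tie pattern among 26 patients gives .67 by these approximations, even if the printed quartiles are ignored.

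**4. Using the printed quartiles as well.** I listed every 15 vs 11 whole-week data set that matches the printed medians and quartiles under any of 11 quartile conventions and has a placebo rank sum of 144.5. The p-value runs from 0.79 to 0.82 without continuity correction and from 0.82 to 0.84 with it (normal or t). Exact permutation p runs from about 0.71 to 0.94, and none rounds to .67. Allowing counts up to 7 does not change this.

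One such data set, by hand:
- Oxytocin: twelve 1s, one 3, two 4s. Placebo: two 0s, five 1s, three 2s, one 3.
- Mid-ranks for 0, 1, 2, 3, 4 are 1.5, 11, 21, 23.5, 25.5.
- Placebo sum = 3 + 55 + 63 + 23.5 = 144.5.
- Σ(t³ − t) = 6 + 4,896 + 24 + 6 + 6 = 4,938, so f = 0.281, variance = 266.8 and SD = 16.33.
- z = 4/16.33 = 0.245, p = 0.81 (0.83 with continuity correction).

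**5. What could produce the printed pair (illustration only).**
- *Misprint in W.* With the SD above, p = .67 needs a deviation of about 0.426 × 16.33 = 7.0, so W near 141.5 or 155.5.
- *Misprint in p.* W = 144.5 with p near 0.8.
- *Fewer patients.* At 13 vs 11 the placebo null mean is 11 × 25/2 = 137.5. Oxytocin with two 0s, nine 1s, two 3s and placebo with two 0s, five 1s, four 2s gives 144.5, SD 15.37, corrected z = 6.5/15.37 = 0.423, p = 0.67. At 13 vs 9 the oxytocin rank sum (null mean 13 × 23/2 = 149.5) can also give both numbers.

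**The case against.** **It is only wording.** The sentence first says that the test was not significant, and the arm sizes, medians and quartiles stand beside it. The protocol's lay summary calls the work preliminary. All this is fair, and a careful reader could discount the conclusion. But the sentence still states absence of effect, and nothing printed measures the difference or its precision.

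**The mismatch may be a slip.** A wrong digit in W or p explains it as well as anything else does. That stands, and it is why the point asks for a correction or an explanation and alleges no cause.

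**A reader might infer that two or more patients were dropped and the intent-to-treat rule broken.** The documents do not support this. No analysed number other than 15 and 11 appears. The dropout rule in section 3.4.3 was written for days, and that section also allows for analyses with missing data. The 13 vs 11 and 13 vs 9 sets only show that fewer patients is one possible explanation. For the same reason, nothing can be said about which arm ranked higher.

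**A reader might infer that the trial missed a real benefit, or that its interval must include 0.8 SD.** That does not follow either. The power of 49 to 52% carries over a planning assumption for another outcome and model, and the interval cannot be recovered from medians and quartiles.

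**Conclusion.** The point holds in two parts. First, the SAP claims no effect on the strength of non-significance alone, in 26 of 50 planned patients, with no between-arm estimate or interval. This part needs no power figure. Second, W = 144.5 and p = .67 cannot both describe a two-sided rank-sum test on all 15 and 11 patients: p should be about 0.79 to 0.84 by normal or t approximation. This assumes whole-week counts and the medians and quartiles as printed; the tie argument in step 3 does not depend on the quartiles. Confidence in the mismatch is high. Its cause is unknown. Either p is far above 5%, so the test stays non-significant. What is at stake is whether the primary result can be reproduced and what may be concluded from it.

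**What to change.** 1. Re-run the Wilcoxon test on all 26 randomised patients. State the number analysed per arm, which arm's rank sum W is, and how weeks with missing status were handled. Correct W or p, or explain each excluded patient against section 3.4.3.
2. Report an effect estimate with a 95% interval. The one that matches the test is the probability that a patient in one arm has the longer run, ties counted half. For placebo with all 26 analysed it is (W − 66)/165, where W is the placebo rank sum, 66 = 11 × 12/2 and 165 = 15 × 11. A bootstrap interval for the mean difference in weeks can be added.
3. Replace the conclusion with wording such as: *No difference was detected in maximum consecutive abstinent weeks (estimate, 95% interval, number analysed per arm). Of the planned 50 patients, 26 were randomised.*

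The cost is one repeated test, one interval and a few sentences; no further patients are needed. The conclusion becomes less definite, and with 11 patients in one arm the interval is itself approximate.
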